12.2 ADVERSE EVENTS REPORTING PROCEDURES

12.2.1 GENERAL

All AEs (e.g., any new event or worsening in severity or frequency of a pre-existing condition or laboratory finding) with an onset date after the subject signs the informed consent for participation in the clinical trial must be promptly documented on the AE eCRF via the electronic data capture (EDC) system. Details of the event must include severity, relationship to study drug(s), duration, action taken, and, for SAEs only, outcome. Whenever possible, reporting specific diagnoses is preferred when reporting AEs in the AE eCRF rather than reporting individual signs and symptoms.

All AEs will be collected from the time the subject signs informed consent through 30 days after receiving the last dose of study drug(s). If initiation of new anticancer therapy occurs within 30 days following the last dose of study drug(s), the date of new anticancer therapy will be recorded on the appropriate eCRF. In addition, the investigator should report any AEs that may occur after this time period which are assessed to have a reasonable possibility of being associated with study drug.

All AEs that are considered related to study drug and all SAEs regardless of relationship to study drug must be followed to resolution or stabilization if improvement is not expected. Adverse events which completely resolve and then recur should be recorded as new AEs. For subjects who complete the EOT visit less than 30 days following the last dose of study drug, a follow-up of ongoing AEs should be documented in the subject's source file. Adverse events continuing at 30 days after the last dose of study treatment should have a comment in the source file by the investigator that the event has stabilized or is not expected to improve.

The investigator is responsible for evaluating all AEs, obtaining supporting source documents, and determining that documentation of the event is adequate. The investigator may delegate these duties to subinvestigators and must ensure that these subinvestigators are qualified to perform these duties under the supervision of the investigator and that they are listed on the FDA Form 1572.

12.3 SERIOUS ADVERSE EVENT DEFINITION

An SAE is an AE that meets 1 or more of the following criteria:

- Death
- Life-threatening experience defined as any adverse experience that places the subject, in the view of the Sponsor or investigator, at immediate risk of death at the time of occurrence (i.e., it does not include a reaction that, had it occurred in a more severe form, might have caused death).
- Requires in-subject hospitalization or prolongation of an existing hospitalization (except scheduled hospitalizations for a nonacute, unrelated cause such as elective surgery).
- Results in persistent or significant disability/incapacity (i.e., substantial disruption in a subject's ability to conduct normal activities of daily living [ADL]).
- Is a congenital anomaly/birth defect in the offspring of an exposed female subject or offspring of a female partner of a male subject.
- Important medical events that may not result in death, be life-threatening, or require hospitalization, may be considered a SAE when, based upon appropriate medical judgment, jeopardizes the subject and may require medical or surgical intervention to prevent 1 of the outcomes listed in this definition.

12.4 SERIOUS ADVERSE EVENT REPORTING AND DOCUMENTATION REQUIREMENTS

Amgen Global Patient Safety must be notified of the occurrence of any SAE within 24 hours of the investigator, designee, or site personnel's knowledge of the event. The SAE will be reported by completing and submitting the SAE report form through the EDC system. In the event that the EDC system is not available, paper SAE report forms may be used to report the SAE to Amgen Global Patient Safety ([Appendix L](#)). Please refer to the SAE Reporting Guidelines in the study reference manual.

Follow-up reports must be submitted in a timely fashion as additional information becomes available.

The investigator is responsible for notifying the Institutional Review Board (IRB) or Independent Ethics Committees (IEC), in accordance with local regulations, of all SAEs. The Sponsor may request for additional source documentation pertaining to the SAE from the investigational site. If a subject is permanently withdrawn from the study due to an SAE, this information must be included in the initial or follow-up SAE report in the eCRF.

The Sponsor is responsible for notifying the appropriate global health authorities of SAEs, when required, in accordance with applicable laws and regulations.

Properly anonymized and de-identified documents (e.g., hospital discharge summaries, autopsy reports, and/or death certificates), as available will be provided to Amgen Global Patient Safety.

12.5 PREGNANCY AND LACTATION EXPOSURE REPORTING

Pregnancy, although not considered an SAE, must be reported to Amgen Global Patient Safety within 24 hours of the investigator's awareness, if the pregnancy has occurred within 30 days of study treatment (for female participants) or within 90 days of study treatment (for female partners of male participants). The pregnancy will be reported on a Pregnancy Notification Worksheet ([APPENDIX M](#)). Amgen Global Patient Safety will follow-up with the investigator regarding additional information that may be requested.

If a subject becomes pregnant while taking an Amgen drug, the study treatment will be immediately discontinued. The investigator will discuss the risks and concerns of investigational drug exposure to a developing fetus and counsel the subject and/or pregnant partner (or ensure that such counseling is provided).

Pregnancies will be followed through the outcome of the pregnancy.

If the outcome of the pregnancy meets a criterion for immediate classification as an SAE (e.g., spontaneous abortion, stillbirth, neonatal death, fetal or neonatal congenital anomaly), the investigator will report the event as an SAE.

With authorization of the subject or female partner, newborns should be followed-up at 6 and 12 months of age.

If a female subject breastfeeds during treatment with carfilzomib or up to 30 days following the last dose of study drug administration, the investigator will notify Amgen Global Patient Safety within 24 hours of learning of her breastfeeding. The investigator will discuss the risks and concerns of breastfeeding while taking an IP. The subject will be required to either discontinue breastfeeding or study treatment. The investigator will complete a Lactation Notification Worksheet ([APPENDIX N](#)). Amgen Global Patient Safety will follow-up with the investigator regarding additional information that may be requested.

12.6 DEATH REPORTING

All deaths that occur from signing of informed consent until 30 days after the last dose of study drug are to be reported as SAEs (unless due to PD - refer to [Section 12.4](#)).

Deaths occurring after the EOT visit do not need to be reported as SAEs. Additional details of the event (such as the primary and contributory causes of death) should be reported on the end of study eCRF.

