APPENDIX B SCHEDULE OF DISEASE ASSESSMENTS

Disease Assessment	Screening (within 21 days of randomization)	Baseline (predose-C1D1)	C1D1	Disease Assessment repeated every 28 days (\pm 4 days)	EOT ^c	LTFU
SPEP/UPEP/immunofixation ^{a,b}	X		X ^b	X	X	X ^d
SFLC ^{a,b}	X		X ^b	X	X	X ^d
Quantitative immunoglobulins ^{a,b}	X		X ^b	X	X	X ^d
Beta-2 microglobulin ^c	X					
Plasmacytoma Evaluation		X ^f				
Skeletal Survey		X ^f				
Bone Marrow Sample ^g						

C1D1 = Cycle 1 Day 1; C2D1 = Cycle 2 Day 1; LTFU = Long-Term Follow-Up; PD = progressive disease; SFLC = serum free light chain; SPEP = serum protein electrophoresis; UPEP = urine protein electrophoresis; EOT = End of Treatment.

- ^a C1D1 before treatment begins (Screening values may be used if obtained within 7 days prior to C1D1) and every 28 days (\pm 4 days) thereafter, at EOT and during LTFU if disease progression has not already been documented, (every 28 days \pm 4 days) until PD and/or start of a subsequent antimyeloma therapy. Refer to [Section 10.2](#).
- ^b Screening values may be used if within 7 days prior to C1D1. Refer to [Section 7](#) for allowable window between randomization and C1D1.
- ^c EOT will be upon treatment discontinuation or early study withdrawal. Refer to [Section 11](#).
- ^d For subjects who did not progress during treatment, SPEP, UPEP, SFLC, and quantitative immunoglobulins will continue to be measured (by the central laboratory) every 4 weeks (every 28 days \pm 4 days) until PD. All subjects will be followed for survival and disease status (if discontinuation is prior to progression) by telephone contact or other method every 12 weeks \pm 28 days for until study closure. Refer to [Sections 10.10.1, 10.10.2 and 11.1](#).
- ^e Must be obtained by central laboratory within 21 days prior to randomization.
- ^f Extramedullary plasmacytoma assessments will be performed if clinically indicated at baseline and repeated during treatment only to confirm a response of PR or better, or to confirm PD, or as clinically indicated. A skeletal survey will be repeated if worsening clinical symptoms suggest PD, or as clinically indicated. Historical plasmacytoma evaluation and a skeletal survey performed within 30 days prior to C1D1 may be used for baseline assessments.

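### Protocol 12.6 both requires and waives an SAE report for a non-PD death that follows the EOT visit but falls within 30 days of the last dose, and its PD cross-reference is wrong

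*Protocol*

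**What the plan says.** Protocol Section 12.6 contains two rules on deaths.

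- The first sets the reporting window: "All deaths that occur from signing of informed consent until 30 days after the last dose of study drug are to be reported as SAEs". Deaths due to PD are excepted, and the reader is sent to Section 12.4 for that exception.
- The second is a waiver: "Deaths occurring after the EOT visit do not need to be reported as SAEs". It does not mention the 30-day window, and it makes no exception for deaths thought to be related to study drug. Causes of death are then to be entered on the end of study eCRF.

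The timing of the EOT visit is given in Appendix B, footnote c: "EOT will be upon treatment discontinuation or early study withdrawal". Appendix A gives EOT a column but no day. Section 12.2.1 has an instruction that begins "For subjects who complete the EOT visit less than 30 days following the last dose of study drug", so the protocol expects that some EOT visits fall inside the 30-day window.

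The other reporting rules run to day 30 or beyond. Section 12.2.1 collects all AEs from consent through 30 days after the last dose. For events after that which may be associated with study drug, it adds that "the investigator should report any AEs that may occur after this time period". Section 12.3 opens with "An SAE is an AE that meets 1 or more of the following criteria", and death is the first criterion listed. Under Section 12.4 the sponsor's safety group "must be notified of the occurrence of any SAE within 24 hours".

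**The concern.** Sites need a single rule for deaths shortly after treatment ends. Section 12.6 appears to give two, one anchored to the last dose and one to the EOT visit. The two anchors are different dates whenever EOT comes before day 30. A site that follows the waiver in good faith may send no SAE report, or a late one, for a death that Sections 12.3 and 12.4 treat as notifiable within 24 hours.

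Safety and tolerability is a secondary endpoint, the DMC reviews safety periodically, and SAP Section 10.6.1 tabulates serious and fatal AEs. Missing reports would leave those tables incomplete for the period just after treatment stops.

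The cross-reference is a separate, clerical matter: a reader who looks up the PD exception is sent to a section that does not contain it.

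**Working it through.** The plan states no figure to reproduce. The check compares the text, with one line of arithmetic for the length of the overlap.

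**Step 1: the two rules in Section 12.6.** Let day 0 be the last dose and let EOT fall on day d.

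| Non-PD death | First rule | Second rule |
|---|---|---|
| Up to and including EOT, by day 30 | Report as SAE | Silent |
| After EOT, by day 30 | Report as SAE | Need not be reported |
| After EOT, beyond day 30 | Silent | Need not be reported |

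The middle row is the conflict. It is empty only if d is 30 or more.

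**Step 2: can d be below 30?** Yes. Appendix B, footnote c ties EOT to treatment discontinuation or early withdrawal, not to day 30. Section 12.2.1 provides expressly for EOT visits earlier than that. No passage requires EOT on or after day 30.

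**Step 3: length of the overlap.** Days with conflicting instructions = max(0, 30 − d). The documents give no value for d, so the values below are assumptions.

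| Assumed d (days) | 0 | 7 | 14 | 21 | 28 | 30 |
|---|---|---|---|---|---|---|
| Days in conflict | 30 | 23 | 16 | 9 | 2 | 0 |

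These are calendar days per subject, not a share of deaths or SAEs. The documents give no basis for a count of deaths.

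**Step 4: the rest of the protocol.** AE collection (12.2.1), the treatment-emergent definition and the planned table of early deaths (both 13.3.3.1) all run to 30 days after the last dose. None stops at EOT, so the waiver is the outlier.

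**Step 5: what remains when d is 30 or more.** Section 12.2.1 asks for later AEs with a reasonable possibility of association with study drug. A late fatal event judged related is reportable under 12.2.1, 12.3 and 12.4, yet the waiver in 12.6 covers it as well. This smaller conflict does not depend on d.

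**Step 6: the cross-reference.** Section 12.4 covers notification within 24 hours, follow-up reports, ethics committee and authority notification, and source documents. It does not mention PD. The rule that deaths from PD go on the death eCRF and are not SAEs is in Section 10.3.3.

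**The case against.** The strongest reply is that the two sentences are not strictly incompatible. The first is mandatory and the second only permissive, so a site that reports the death complies with both. The fatal event should also reach the safety database by another route. The SAE form in Appendix L treats death as an outcome and asks for its cause, while 12.2.1, 12.3 and 12.4 make a fatal AE within 30 days collectable, serious and notifiable whatever 12.6 says. The study reference manual cited in 12.4, which is not among the documents, may settle the matter. The consequence is in any case small.

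Part of this stands. The fault is an over-broad waiver rather than two duties that cannot both be met, and the consequence is limited. The objection does not remove the conflict, however. A site may act on an express statement that no SAE report is needed, and the general rules in 12.2.1 to 12.4 contradict that statement without saying that they override it. A manual that has not been seen cannot be relied on to cure the protocol text.

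The wrong section number is indeed editorial: 12.6 states the PD exception itself, so a reader can apply it without the reference. It adds no weight to the main point.

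**Conclusion.** The point holds. For a non-PD death after EOT and by day 30, Section 12.6 requires an SAE report and then waives it, and nothing in the protocol or SAP reconciles the two. The overlap lasts 30 − d days when d is below 30. Its practical size is unknown, because neither d nor the number of such deaths is given.

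The consequence is confined to expedited reporting and to the completeness of the serious-AE and fatal-AE tables. Causes of death still go on the end of study eCRF, the table of deaths within 30 days of last administration can be built from dates, and PFS and OS are not affected. This should be fixed, but it does not threaten the trial's conclusions. Confidence in the textual conflict is high. How sites would act on it cannot be judged from the documents.

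**What to change.** Replace the waiver in Section 12.6 with wording such as: *A death more than 30 days after the last dose of study drug requires no SAE report unless it is considered related to study drug.* This introduces no new rule: the 30-day limit and the reporting of later related events are already in Section 12.2.1, and relatedness is defined in Section 12.1.4. It also removes the smaller conflict over late related deaths.

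Keep the PD exception and change its cross-reference from Section 12.4 to Section 10.3.3.

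The cost is one sentence and one cross-reference in a protocol amendment, plus a note to sites. Any additional SAE reports for deaths by day 30 would be ones that the first sentence of 12.6 already requires.

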13 STATISTICAL CONSIDERATIONS

This section describes the statistical considerations of the study design and summarizes the statistical analyses that will be conducted to assess the efficacy and safety endpoints in the study. Further details will be provided separately in the Statistical Analysis Plan (SAP). If, after the study has begun, but prior to the final analysis, important changes are made to the primary or key secondary analyses, then the changes will be reflected in the SAP or its amendment where applicable. The study protocol may be amended as appropriate. Any other changes made to the planned analyses after the protocol and SAP have been finalized, along with an explanation as to when and why they occurred, will be described in the clinical study report, in which any post hoc exploratory analyses also will be clearly identified. Any changes made in the analysis plan, after the primary inferential comparisons between treatment groups are performed, will be exploratory in nature.

13.1 STUDY ENDPOINTS

13.1.1 *PRIMARY ENDPOINTS*

The primary endpoint is **PFS**, which is defined as **the time in months from randomization to the earlier of disease progression or death due to any cause.**

13.1.2 *SECONDARY ENDPOINTS*

The secondary endpoints of the study are as follows:

- **ORR**, defined as the **proportion of subjects who achieved a confirmed PR, VGPR, CR, or sCR, according to the IMWG-URC.**
- OS defined as the time in months from randomization to death due to any cause.
- Safety and tolerability
- Sparse PK

13.2 STUDY POPULATIONS

13.2.1 *INTENT-TO-TREAT POPULATION*

The Intent-to-Treat (ITT) Population consists of all randomized subjects. It will be the basis for the analysis of efficacy endpoints in this study. Subjects in the analysis based on the ITT Population will be included in the treatment group to which they were randomized.

13.2.2 *SAFETY ANALYSIS POPULATION*

The Safety Population is defined as all randomized subjects who received at least 1 dose of any study drug (i.e., carfilzomib, dexamethasone). Subjects in the analysis based on the Safety Population will be included in the treatment group corresponding to the actual treatment received.

13.3 STATISTICAL METHODS

13.3.1 *ANALYSIS OF THE CONDUCT OF THE STUDY*

The number of subjects screened, randomized, and treated will be presented. The number and percentage of subjects excluded from each analysis population will be summarized with reasons for exclusion. The number of subjects who discontinue study treatment will be tabulated, along with the reason for discontinuation.

Subjects' demographics and baseline characteristics, disease characteristics, prior and concomitant medications, and study drug exposure and treatment compliance will be summarized descriptively for each treatment group.

The number and percentage of subjects with important protocol deviations will be summarized by treatment group.

13.3.2 EFFICACY ANALYSES

All efficacy analyses will be based on the ITT Population, which consists of all subjects randomized.

13.3.2.1 Primary Efficacy Endpoint

The primary efficacy endpoint is PFS. Progression-free survival will be calculated from the time of randomization until disease progression or death due to any cause, whichever occurs first. If a subject is alive or lost to follow-up without experiencing documented disease progression by the data cutoff date, the PFS data for the subject will be censored at the date of last valid disease and response assessment. Detailed PFS data censoring rules will be described in the SAP.

The distribution of PFS, including median, will be estimated using the Kaplan-Meier method. Progression-free survival rates at selected time points will be reported by treatment group. The 95% CI for the median and other percentiles of PFS will be constructed using the method of [Klein and Moeschberger \(1997\)](#) with log-log transformation. The 95% CIs for PFS rates were estimated using the method by [Kalbfleisch and Prentice \(1980\)](#) with log-log transformation. The inferential comparison between treatment groups will be made using the log-rank test stratified by the randomization stratification factors specified in [Section 7](#). The hazard ratio (HR) and its 95% CI will be estimated using a Cox proportional hazards model stratified by the same randomization stratification factors. Duration of follow up for PFS will be estimated using the reverse Kaplan-Meier method ([Schemper 1996](#); [Smith 2006](#)).

Response and disease progression will be determined using a validated computer algorithm (Onyx Response Computational Assessment; [ORCA]), as well as by local

investigators and an Independent Review Committee (IRC). The primary analysis of PFS will be based on ORCA-assessed outcomes. The PFS outcomes assessed by the investigator will serve as a supportive analysis of PFS, as will IRC-assessed outcomes.

The final PFS analysis will be conducted when approximately 350 PFS events have occurred or by end of year 2018, whichever is earlier. A total of 350 PFS events will provide 83% power to detect a significant difference in PFS between the 2 treatment groups with 1 interim analysis ^{CCI} [REDACTED]. The interim analysis will be performed when 75% of the total PFS events (i.e., 263 events) have occurred. See also Section 13.8 for the interim analysis plan for PFS.

13.3.2.2 Secondary Efficacy Endpoints

13.3.2.2.1 Overall Response Rate

The ORR will be analyzed at the time of the PFS analysis (interim or final), only if the PFS analysis crosses the boundary. The inferential comparison of ORR between treatment groups will be made using a logistic regression model-based test against the null hypothesis that the odds ratio is ≤ 1 at a 1-sided significance level of 0.025. The regression model will include the randomization stratification factors as covariates. The ORR will be calculated by treatment group and the associated 95% CI will be estimated using the Clopper-Pearson method. The odds ratio (and its 95% CI) will be estimated using the logistic regression model.

The primary analysis of ORR will be based on the ORCA-assessed responses. Investigator assessed responses will be analyzed as a supportive analysis of ORR, as will IRC-assessed responses.

The duration of response (DOR), defined as time in months from the start date of the response to the earlier date of documented disease progression or death, will be calculated for subjects who achieve sCR, CR, VGPR, or PR. The DOR will be censored at date of the last valid assessment for responders who have not experienced disease progression or death. The distribution of DOR, including the

median, will be estimated using the Kaplan-Meier method on the basis of subjects who achieve overall response.

13.3.2.2.2 Overall Survival

Overall Survival will be analyzed using the same methods as for PFS.

Overall Survival data will be right-censored at the earlier of last known alive date or data cutoff date for subjects who are still alive.

The analysis of OS will be conducted at the time of the PFS analysis (interim or final), only if both PFS and ORR analyses are positive, per hierarchical testing procedures. There will be no interim analysis for OS. Additional follow-up for OS may be performed.

